2.1 Objectives and Endpoints

Objectives	Endpoints
Primary	

To evaluate the pharmacokinetics (PK) of AMG 986 following the administration of a single oral 200 mg dose to healthy volunteers and subjects with severely impaired renal function	
AMG 986 PK parameters including area under the plasma concentration time curve from time 0 to the time of the last quantifiable sample (AUC_{0-t}) and maximum observed plasma concentration after dosing (C_{max}).Additional AMG 986 PK parameters may include but not limited to terminal phase half-life ($t_{1/2}$); time of maximum AMG 986 plasma concentration (t_{max}); and AUC from time 0 to infinity (AUC_{inf})
Secondary	

To evaluate the safety and tolerability of AMG 986 following single oral dose administration to subjects with severely impaired renal function relative to healthy matched control subjects	
Subject incidence of adverse events and clinically significant changes in vital signs, physical examinations, clinical laboratory tests, and ECGs
Exploratory	

To determine unbound concentrations of AMG 986 in plasma	
Plasma protein binding of AMG 986

To determine AMG 986 metabolite concentrations in plasma	
AMG 986 metabolite concentrations in plasma

2.2 Clinical Hypotheses

Clinically significant changes in AMG 986 PK that would require dose adjustment are not expected in subjects with severe renal impairment when compared to subjects with normal renal function.

3. Study Overview

3.1 Study Design

This is a phase 1, multicenter, open-label, single-dose study conducted in subjects with severely impaired renal function as determined by the modification of diet in renal disease (MDRD) equation for estimated glomerular filtration rate (eGFR). Approximately 12 subjects will be assigned to the two groups in the study. Approximately 6 subjects with severely impaired renal function (eGFR 15 to 29 ml/min/1.73 m²) will be assigned to group 1; approximately 6 subjects with normal renal function (eGFR \geq 90 mL/min/1.73 m²) will be assigned to the control group 2. All subjects in each group will receive a single oral dose of 200 mg AMG 986.

An attempt will be made to match the control group of healthy males and females with normal renal function (group 2) to the group of subjects with severely impaired renal function (group 1) by age range, body weight range, gender (proportion of male and female subjects), and race. Enrollment of subjects in the control group will be initiated after all subjects in the renal impairment (RI) group have been enrolled. The mean age \pm 5 years and mean body weight \pm 10% of the subjects in the RI group will be used to help match the subjects in the control group. The priority for matching subject characteristics of the two groups will be: age range, body weight range, gender, then race.

3.2 Sample Size

This is a Phase 1 study and no formal statistical hypothesis testing will be performed. The study is designed to characterize AMG 986 PK and safety plus tolerability, following a single oral administration of a 200-mg dose by descriptive summaries based on the observed data. The sample size of this study is based on practical considerations and is consistent with the number of subjects enrolled in similar studies. Approximately 12 subjects (6 subjects with severe RI and 6 subjects with normal renal function) will be enrolled for the study. Assuming 20% for the intra-subject standard deviation for AMG 986 log-transformed PK parameters (AUC_{0-t} and C_{max}) and assuming that it is the same in the 2 groups, the current sample size of 6 would provide a Confidence Interval for the Geometric Mean Ratio of the parameters of (0.81, 1.23). For safety

considerations, with a total of 12 subjects receiving AMG 986, there is a 46% chance of detecting an adverse event with a true incidence of 5% and a 72% chance of detecting a more common adverse event with a true incidence rate of 10%.

4. Covariates and Subgroups

4.1 Planned Covariates

Baseline values may be used as a covariate in analyses. For any variable, unless otherwise defined, baseline is defined as the last assessment taken prior to the first administration of AMG 986.

Group 1 will be the group formed with subjects with severely impaired renal function. Group 2, the group formed with subjects with normal renal function, will be considered the control group. An effort will be made to match the subjects in group 2, the normal renal function group to the subjects in group 1, by age range, body weight, gender, and race. The mean age \pm 5 years and mean body weight \pm 10% of the subjects in the severely renal impaired group will be used to help match the subjects in the control group.

4.2 Subgroups

No subgroup analyses are planned for this study.

5. Definitions

Age at Enrollment

Subject age at enrollment will be collected in years in the clinical database.

AUC

Area under the plasma AMG 986 concentration-time curve.

AUC₀₋₂₄

Area under the concentration-time curve from time 0 extrapolated to 24 hours.

AUC_{inf}

Area under the concentration-time curve from time 0 extrapolated to infinity.

Baseline

Baseline is defined as the last assessment taken prior to the first administration of AMG 986.

C_{max}

Maximum observed plasma AMG 986 concentration.

Baseline ECG recording

Baseline ECG recording is defined as the mean of the 3 sets of triplicate ECG results at day 1 pre-dose (a total of 9 assessments).

Body Mass Index

Body Mass Index (BMI) will be calculated using height and weight measurements taken at screening and using the following formula:

$$\text{BMI (kg/m}^2\text{)} = \text{weight (kg)} / [\text{height (cm)} / 100]^2$$

End of Study

The end of study date is defined as the date when the last subject is assessed or receives an intervention for evaluation in the study (i.e. last subject last visit), following any additional parts in the study (e.g. long-term follow-up), as applicable.

End of Study for Individual subject

The end of study for individual subject is defined as the last day that protocol-specified procedures are conducted for an individual subject.

End of Study Visit

Subjects will return to the clinic for follow-up visits in accordance to the Schedule of Assessments and be followed through the completion of the End of Study (EOS) procedures on study day 30. If an EOS test result demonstrates a clinically significant clinical or laboratory abnormality, the subject will be followed until resolution of the abnormality or until it is considered clinically stable by the Investigator.

End of Treatment

The end of treatment is defined as the last assessment for the protocol specified treatment phase of the study for an individual subject.

Estimated Glomerular Filtration Rate

For determining eligibility, estimated glomerular filtration rate (eGFR) will be calculated by the estimated Modification of Diet in Renal Disease (MDRD) formula based on serum creatinine, age, sex, and race values at time points indicated in the Schedule of Assessments. The Glomerular Filtration Rate (GFR) will be estimated as

eGFR in mL/min per 1.73 m² = 175 x SerumCr-1.154 x age-0.203 x 1.212 (if patient is black) x 0.742 (if female).

Investigational Product

Investigational product refers to AMG 986 in this study.

Primary Completion

The primary completion is defined as the date when the last subject is assessed or receives an intervention for the final collection of data for the primary endpoint(s), for the purposes of conducting the primary analysis, whether the study concluded as planned in the protocol or was terminated early.

Study Day 1

The study day 1 is defined as the first day that protocol specified investigational product(s) /protocol-required therapies is/are administered to the subject.

Half-life (t_{1/2})

The time required for the observed concentration of a drug to be reduced by one-half.

T_{max}

The time of maximum observed plasma AMG 986 concentration.

Treatment-Emergent Adverse Event

Events categorized as Adverse Events (AEs) starting on or after first dose of investigational product as determined by the flag indicating if the adverse event started prior to the first dose on the Events CRF and up to and including 30 days after the end of investigational product or the End of Study date, whichever is earlier.

6. Analysis Sets

For all analyses, subjects will be analyzed according to the group they were assigned.

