9.2 Safety Event Reporting Procedures

9.2.1 Adverse Events

9.2.1.1 Reporting Procedures for Adverse Events That do not Meet Serious Criteria

The investigator is responsible for ensuring that all adverse events observed by the investigator or reported by the subject that occur after dose of investigational product through the Safety Follow-Up Visit/End of Study Visit are reported using the Event CRF.

The investigator must assign the following adverse event attributes:

- Adverse event diagnosis or syndrome(s), if known (if not known, signs or symptoms),
- Dates of onset and resolution (if resolved),
- Severity [and/or toxicity per protocol],
- Assessment of relatedness to investigational product (AMG 986), and/or any study-mandated activity/procedure(s), and
- Action taken

The adverse event grading scale used will be the Common Terminology Criteria for Adverse Events (CTCAE) version 4. The grading scale used in this study is described in [Appendix A](#).

The investigator must assess whether the adverse event is possibly related to the investigational product (AMG 986). This relationship is indicated by a “yes” or “no” response to the question: Is there a reasonable possibility that the event may have been caused by the investigational product? Relatedness means that there are facts or reasons to support a relationship between investigational product and the event.

The investigator must assess whether the adverse event is possibly related to any study mandated activity (eg, administration of investigational product, protocol-required therapies, use of medical device(s) and/or procedure (including any screening procedure(s))). This relationship is indicated by a “yes” or “no” response to the question:

“Is there a reasonable possibility that the event may have been caused by a study activity (eg, administration of investigational product, protocol-required therapies, use of medical device(s)), and/or procedure”?

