9.6 Safety Analyses

9.6.1 Adverse Events

The Medical Dictionary for Regulatory Activities (MedDRA) version 20.1 will be used to code all events categorized as adverse events (AE) to a system organ class and a preferred term. The CTCAE version 4.0 will be used to grade severity of adverse events unless specified otherwise. Treatment-emergent adverse events are events with an onset after the administration of the first dose of investigational product.

The subject incidence of adverse events will be summarized for all treatment-emergent adverse events, serious adverse events, and fatal adverse events.

Subject incidence of all treatment-emergent adverse events, serious adverse events, adverse events leading to withdrawal of investigational product, and fatal adverse events will be tabulated by system organ class and preferred term in alphabetical order.

Subject incidence of events of interest (standardized MedDRA queries and/or Amgen customized queries) will also be summarized according to their categories and preferred term. Summaries of treatment-emergent and serious adverse events will be tabulated by system organ class, preferred term, and grade.

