Appendix A. Imputation Rules for Partial or Missing Stop Dates

If the month and year are present, impute the last day of the month. If only the year is present, impute December 31 of that year. If the stop date is entirely missing, assume the event or medication is ongoing. If a partial or complete stop date is present and the 'ongoing' or 'continuing' box is checked, then it will be assumed that the AE or conmed stopped and the stop date will be imputed, if partial.

Imputation Rules for Partial or Missing Start Dates.

Start Date		Stop Date						Missing
		Complete: yyyyymmdd		Partial: yyyyymm		Partial: yyyy		
		< 1 st Dose	≥ 1 st Dose	< 1 st Dose yyyyymm	≥ 1 st Dose yyyyymm	< 1 st Dose yyyy	≥ 1 st Dose yyyy	
Partial: yyyyymm	= 1 st Dose yyyyymm	2	1	2	1	N/A	1	1
	≠ 1 st Dose yyyyymm		2		2	2	2	2
Partial: yyyy	= 1 st Dose yyyy	3	1	3	1	N/A	1	1
	≠ 1 st Dose yyyy		3		3	3	3	3
Missing		4	1	4	1	4	1	1

- 1 = Impute the date of first dose
- 2 = Impute the first of the month
- 3 = Impute January 1 of the year
- 4 = Impute January 1 of the stop year

Note: For subjects who were never treated (first dose date is missing), partial start dates will be set to the first day of the partial month.

Note: If the start date imputation leads to a start date that is after the stop date, then do not impute the start date.

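### Do the two wordings of the treatment-emergent adverse event rule in the SAP (Sections 5 and 9.6.1) put the safety tables at risk?

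*SAP*

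**What the plan says.** SAP Section 5 (Treatment-Emergent Adverse Event) has a start and an end. The start is on or after first dose, decided by the Events CRF flag for onset before dosing. The window then runs "up to and including 30 days after the end of investigational product or the End of Study date, whichever is earlier".

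SAP Section 9.6.1 says: "Treatment-emergent adverse events are events with an onset after the administration of the first dose of investigational product". It mentions no flag and no end. On the tables it adds: "The subject incidence of adverse events will be summarized for all treatment-emergent adverse events, serious adverse events, and fatal adverse events".

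Section 5 also holds two end-of-study terms. One is study-level: "The end of study date is defined as the date when the last subject is assessed". The other is for the individual: "The end of study for individual subject is defined as the last day that protocol-specified procedures are conducted for an individual subject". The treatment-emergent rule uses the first.

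The protocol uses the term treatment-emergent in Section 10.4.3.1.1 but does not define it. Its collection windows are:

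- Non-serious events (Section 9.2.1.1): those that "occur after dose of investigational product through the Safety Follow-Up Visit/End of Study Visit are reported using the Event CRF".
- Serious events (Section 9.2.1.2 and Schedule of Assessments footnote 6): from consent to 30 days after dosing or the end-of-study visit, whichever comes later.

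**The concern.** A plan that defines the same term twice, without saying which definition governs, leaves a choice to the programmer. Three differences stand out.

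- **Start.** Section 5 says on or after, with a flag. Section 9.6.1 says after, without one. Protocol Section 9.2.1.1 lists onset dates, not times, among the attributes the investigator must assign, and SAP Appendix A sends many incomplete start dates to the dosing day ("1 = Impute the date of first dose"). If someone coded Section 9.6.1 as onset date later than dose date, every Day 1 event would drop out.
- **End.** Section 5 takes the earlier of two dates, the protocol's serious-event rule takes the later of two, and Section 9.6.1 has no limit.
- **Cut-off term.** The end-of-study date in the rule is defined for the whole study, although a subject-level term was available.

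Subject incidence of adverse events is the secondary endpoint, and each group has about six subjects. If the definitions truly diverged, the same data could give two different tables.

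**Working it through.** The plan states no figure for this point, so the check compares the texts and counts days.

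**Start rule**

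1. Each subject receives one dose, on Day 1 (Protocol Section 5.1). The reference in Section 9.6.1 is the administration of that dose, not its calendar date.
2. An event that the CRF flag marks as not pre-dose is therefore an event after administration. The two wordings pick out the same events.
3. Non-serious events are to be reported only if they occur after the dose (Protocol Section 9.2.1.1; Schedule of Assessments footnote 5). A non-serious event recorded on Day 1 is already post-dose by the collection rule.
4. Serious events are collected from consent, so the pre-dose question matters mainly for them. The sample contingency form in Protocol Appendix B has a box for onset before first dose.
5. Appendix A assigns uncertain starts to the dosing day. That convention makes sense only if dosing-day events count, so the SAP already shows which start rule it means.

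**End rule**

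Inputs: dose on Day 1, so dose + 30 days is Day 31; end-of-study visit on Day 30 (Protocol Section 7.2.4).

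- Section 5 end = min(31, E), where E is last subject last visit (literal reading) or the subject's own end of study (alternative reading).
- Non-serious collection end = end-of-study visit.
- Serious collection end = max(31, end-of-study visit).
- Gap = collection end − Section 5 end, or 0 if negative.

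| Case | Non-serious gap | Serious gap, study-level E | Serious gap, subject-level E |
|---|---|---|---|
| Visit on Day 30 (planned) | 0 | 31 − 31 = 0 | 31 − 30 = 1 |
| Visit on Day 30 that is also the study's last visit | 0 | 31 − 30 = 1 | 1 |
| Visit on Day 33 (assumed) | 33 − 31 = 2 | 2 | 2 |
| Visit on Day 37 (assumed) | 37 − 31 = 6 | 6 | 6 |
| Exit on Day 8 (assumed) | 0 | normally 31 − 31 = 0 | at most 31 − 8 = 23 |

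The late-visit rows are assumptions. Protocol Section 7.2 gives deviation windows only through Day 6, but Section 3.5.1 puts the on-study period at up to 30 days, so a visit after Day 31 would be off plan. The 23-day figure needs the subject-level reading, and it is an upper limit because a subject who has left may yield no further reports.

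**Relevance of the last day**

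Mean half-lives after oral dosing in healthy subjects were 13.2 to 18.0 hours (Protocol Section 2.2.2). Thirty days is 30 × 24 = 720 hours, and 720 / 18.0 = 40 half-lives at the slow end. The half-life in severe renal impairment is not given. Even if it were three times as long (an assumption), 720 / 54 is about 13 half-lives. Whether Day 31 counts has little bearing on drug effect.

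**The case for a change.** The best case for a change is that the fix is cheap and the ambiguity is real. Section 9.6.1 reads as a complete definition and sits where the tables are specified. The study is open-label, so a rule settled before database lock removes any later choice. With six subjects in a group, one reclassified subject moves incidence by 1/6 = 16.7 percentage points. No visit window protects the Day 30 visit. SAP Section 9.6.1 also leaves open whether the serious and fatal event tables are limited to treatment-emergent events.

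Some of this stands. The wordings differ, there is no cross-reference, and the end-of-study term could have been clearer. A late visit would leave a few collected days outside Section 5.

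The rest is weaker. One-sixth is the weight of any event in any group of six and says nothing about how often the definitions disagree. The Day 1 loss requires a programmer to ignore the flag, read administration as a calendar date and discard the whole dosing day. The premise that onset times are missing is not established either: the Event CRF itself is not in the documents, and Protocol Section 6.2.1.1 requires the time of emesis and diarrhea to be noted on it. On the end rule, the SAP does not give two competing dates. One section gives a date and the other gives none. A treatment-emergent window slightly shorter than the serious-event reporting window is not an error in itself.

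**Conclusion.** The inconsistency is real but clerical, and no change to the plan follows. Section 5 is the definitions section and holds the full rule. Section 9.6.1 reads naturally as a short form of it, and an analyst would program Section 5 with the flag. Either wording, followed as written, gives a sound table.

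The start rules do not differ in substance for a single-dose study. On the planned schedule the end rules differ by 0 days for non-serious events and by 0 to 1 day (Day 31) for serious events. Safety is summarised descriptively, with no hypothesis test (SAP Section 3.2), and the primary pharmacokinetic comparison is not involved.

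This rests on two assumptions: the CRF flag is completed, and end-of-study visits take place at or close to Day 30. If a visit fell after Day 31, the gap would equal the days beyond Day 31. Those events would still have been collected, and SAP Section 6.1 refers to an adverse event listing for all enrolled subjects, so they should remain visible even if left out of the treatment-emergent table.

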6.1 Safety Analysis Set

The safety analysis set will consist of all study subjects who receive at least one dose of AMG 986. Subjects withdrawing prior to AMG 986 administration due to adverse events related to study procedure will not be included in the safety analysis set but those adverse events will be included in the adverse events listing for all enrolled subjects.

6.2 Pharmacokinetic (PK) Analyses Set

The PK analysis set will consist of all subjects for whom at least one PK parameter or endpoint can be estimated.

7. Planned Analyses

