3.4 Replacement of Subjects

Enrolled subjects who do not receive AMG 986 or do not receive the full dose of AMG 986 may be replaced. Subjects who drop out of the study for reasons other than adverse events or serious adverse events after receiving investigational product may be replaced at the discretion of Amgen in consultation with the investigator or their designee.

All data from any replaced subjects will be captured and kept in the clinical trial database and identified as such.

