6.2.1.1 Dosage, Administration, and Schedule

Subjects will be admitted to the study clinic on day -1 and will remain resident until completion of all study procedures 24 hours after dosing until day 2.

On day 1, enrolled subjects will receive IP (200 mg AMG 986) by oral administration on an empty stomach (no food or liquids, except water, for at least 8 hours prior to dose administration) on study day 1. Subjects will remain in a fasted state (no food or liquids,

except water) for at least 2 hours after dose administration. Fasting instructions will apply to both treatment groups. Following completion of all study procedures on day 2 (see [Schedule of Assessments](#)), subjects will be discharged from the clinic with instructions to return to the research facility at specified time points for collection of blood samples for PK assessments and completion of safety assessments through the end of the study.

Emesis and diarrhea will be documented in the subject source and on the Event CRF, with time and severity of the event noted. Any subject who experiences emesis within 4 hours of dosing may be excluded from the pharmacokinetic analysis. Any subject who experiences diarrhea within 24 hours of dosing may be excluded from the pharmacokinetic analysis.

The effects of overdose of this product are not known.

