10.1.2.2 Pharmacokinetic (PK) Analysis Set

The PK analysis set will consist of all subjects for whom at least one PK parameter or endpoint can be reliably estimated.

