9.1 General Considerations

Descriptive statistics will be provided for selected demographics, adverse events, vital signs, ECG, PK, and laboratory measurements. Descriptive statistics on continuous data will include means, medians, standard deviations, and ranges, while categorical data will be summarized using frequency counts and percentages. Graphical summaries of the data may also be presented. When data are summarized by time, the values recorded against the scheduled time points listed in the protocol will be used. When assessing minimum/maximum increases or decreases over the study, all assessments, including unscheduled assessments will be used. All data analysis will be conducted using subjects in the safety analysis set except for pharmacokinetic analysis, which will be conducted using PK analysis set. For statistical analyses comparing change from baseline, only subjects with both baseline and at least one post-baseline assessment will be included. The primary analysis will occur after the database lock following last subject last visit.

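### Does the SAP's dropped word 'reliably' let a vomited or part-taken dose into the primary GMR as a full 200 mg observation?

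*SAP*

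**What the plan says.** The two definitions of the PK analysis set differ by one word. SAP 6.2: "The PK analysis set will consist of all subjects for whom at least one PK parameter or endpoint can be estimated". Protocol 10.1.2.2 takes subjects "for whom at least one PK parameter or endpoint can be reliably estimated". Neither document defines *reliably*, and SAP 10 says that the protocol's analyses are unchanged.

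SAP 9.1 applies the safety set throughout, "except for pharmacokinetic analysis, which will be conducted using PK analysis set". SAP 9.7.1 then fits an ANOVA to the log-transformed parameters with renal function group as the only term. It uses actual dosing and sampling times but does not adjust for the amount taken.

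The provisions on compromised doses are in the protocol. Section 6.2.1.1 says: "Any subject who experiences emesis within 4 hours of dosing may be excluded from the pharmacokinetic analysis", and "Any subject who experiences diarrhea within 24 hours of dosing may be excluded from the pharmacokinetic analysis". Both kinds of event go on the Event CRF "with time and severity of the event noted". Under Section 3.4, enrolled subjects who are not dosed or "do not receive the full dose of AMG 986 may be replaced", and "All data from any replaced subjects will be captured and kept in the clinical trial database and identified as such". The SAP repeats none of this.

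**The concern.** The dropped word is the only quality standard in the set definition. Without it, any subject with one estimable parameter belongs to the set, including one who vomited soon after dosing or swallowed only some of the tablets. Such a profile would count as a 200 mg observation. A subject replaced under Protocol 3.4 could also be counted alongside the replacement.

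With six subjects per group, one bad profile matters. A low value in group 1 lowers the GMR and so hides an increase in exposure, which is what the study is meant to detect. A low value in group 2 raises it. The protocol's exclusions are optional and carry no criterion or timing, in an open-label study. Two analysts could therefore build different sets and report different primary estimates.

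**Working it through.** **1. The plan's own figure.** Inputs from SAP 3.2 and 9.7.1: log-scale SD 0.20, 6 v 6, 90% interval, true ratio taken as 1.

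- Half-width = t(0.95, 10) × SD × sqrt(1/6 + 1/6) = 1.812 × 0.20 × 0.577 = 0.209.
- exp(±0.209) = (0.811, 1.233), which reproduces the stated (0.81, 1.23).

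**2. One compromised profile kept in.** The documents give no size for such a loss, so 10%, 25% and 50% are assumptions. For scale, 200 mg is eight 25 mg tablets (Protocol 6.2.1). Two or four tablets missed is a 25% or 50% loss if exposure is proportional to dose, which Protocol 2.4 calls apparent but not formally evaluated.

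- GMR multiplier, group 1: (1 − loss)^(1/6). Group 2: its inverse.
- Expected half-width: 1.812 × sqrt([10 × SD² + (5/6) × ln(1 − loss)²]/10) × sqrt(2/6).

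| Loss | Group 1 multiplier | Group 1 90% CI | Group 2 multiplier | Group 2 90% CI |
|---|---|---|---|---|
| 10% | 0.983 | (0.80, 1.21) | 1.018 | (0.82, 1.26) |
| 25% | 0.953 | (0.76, 1.20) | 1.049 | (0.84, 1.32) |
| 50% | 0.891 | (0.66, 1.20) | 1.122 | (0.84, 1.51) |

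If the subject is kept beside a replacement (7 v 6), the group 1 multipliers for 25% and 50% are 0.960 and 0.906.

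**3. Shift against the planned uncertainty.** The log shifts are 0.018, 0.048 and 0.116.

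- At SD 0.20, these are 8%, 23% and 55% of the half-width of 0.209.
- The 33% CV for AUCinf at 200 mg in Protocol Table 1 gives SD = sqrt(ln(1 + 0.33²)) = 0.32. The half-width is then 0.336, and the shares fall to 5%, 14% and 34%.

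**4. Excluding the subject without replacement (5 v 6).** 1.833 × 0.20 × sqrt(1/5 + 1/6) = 0.222, giving (0.80, 1.25). With a replacement it is (0.81, 1.23) again.

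**5. Does the missing word cause the problem?** Take each kind of subject in turn.

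- *Emesis or diarrhea in the windows.* Protocol 6.2.1.1 permits exclusion from the PK analysis. SAP 1 says the SAP details the analyses outlined in the protocol, and SAP 10 declares no change. Not repeating a provision does not cancel it, so the permission holds whichever wording of the set is used.
- *Part dose.* AUC and Cmax can be estimated reliably for whatever was swallowed. Putting *reliably* back would not clearly remove this subject.
- *Replaced subject.* The handling turns on Protocol 3.4, not on estimability. The data are flagged in the database.

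Membership also rests on at least one parameter per subject. It does not require every parameter from that subject to enter the GMR.

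**6. Other provisions.** SAP 8.3 excludes incomplete primary endpoint data. SAP 8.5 allows exclusion with scientific justification. SAP 9.2 reviews a listing of set membership for all enrolled subjects. SAP 8.4 and 9.3 track important deviations by group.

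**The case for a change.** The strongest reply is that none of these provisions is a rule.

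- A subject who vomited but was fully sampled has complete endpoint data, so SAP 8.3 need not apply.
- SAP 8.5 keeps confirmed outliers by default, and a 25% loss is 0.288 on the log scale: 1.4 SD at 0.20, or 0.9 SD at 0.32. It would not stand out.
- Protocol 10.3.1 plans no data review meeting at which exclusions would be settled.
- The bias in group 1 runs the wrong way: a true GMR of 1.50 would appear as 1.43 after a 25% loss, or 1.34 after 50%.

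All of this is correct as far as it goes. Nor does the case rest on such events being rare. In the first-in-human data (Protocol 2.3) the commonest adverse event was headache, in 5 of 72 subjects, so vomiting and diarrhea were each reported in no more than 5. That ceiling is loose: at 5/72 per subject, the chance of at least one event of a given type among 12 is 1 − (67/72)^12 = 58%. Those subjects were also healthy, and routes and doses were mixed.

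But analysts do not need the value to look like an outlier in order to act. The time and severity of emesis and diarrhea are recorded, staff give the dose, and replaced subjects are identified. The information needed for a judgment is at hand, and SAP 9.2 makes the outcome visible. With median Tmax of 1.0 to 2.0 hours (Protocol 2.2.2), many events late in the 4-hour and 24-hour windows would cost little exposure. A fixed rule would also have to choose between exclusion and dose-normalization for part doses, and both are defensible.

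**Conclusion.** The concern does not call for a change. The wording of SAP 6.2 is a clerical departure from Protocol 10.1.2.2, and restoring an undefined adverb would not by itself alter any result. The substantive gap, how to treat part-dosed and replaced subjects and when to use the optional exclusions, exists in both documents. It is the kind of detail that PK analysts settle sensibly from recorded facts.

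If such an event occurred and the profile were kept unadjusted, the GMR would move by about 2%, 5% or 11% to 12% for a loss of 10%, 25% or 50% in one of six subjects. At SD 0.20 the first two shifts are at most 23% of the CI's log half-width. Only the assumed loss of half the exposure reaches 55%. These figures assume a true ratio of 1, one affected subject and hypothetical losses. The study plans no formal hypothesis test, so no formal conclusion would reverse. The planned sample size and the stated interval are unaffected.
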